### **Purpose of the Study**

The goal of our study is to determine whether prehospital use of a commercial pelvic binder will improve morbidity and mortality in patients with pelvic fractures. We hypothesize that prehospital placement of pelvic binders will reduce hemorrhage and need for resuscitation and will improve overall mortality in patients with pelvic fractures. Our primary outcomes will be indicators of hemorrhage (including vital signs, lactate, base excess, volume of blood products required for resuscitation, need for angioembolization or surgical control of bleeding, and length of ICU stay) and 30-day mortality. We will also measure safety events related to binder use. Additionally, we hypothesize that pelvic splinting via external compression will improve patients' pain regardless of whether they have a pelvic, acetabular, or proximal femur fracture. Pain control in the prehospital environment will be addressed as a secondary outcome in this study.

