**PATCH – Pelvis Protocol v5**  
**12/20/16**

- (2) Traumatic injury other than ground-level fall (e.g. MVC, MCC, fall from height  $\geq 20$  feet, etc.), *and*
- (3) Complaint of pelvic, groin, or hip pain, *or*
- (4) Pelvic or hip deformity, ecchymosis, or crepitus in an obtunded patient, *or*
- (5) Hemodynamic instability:
  - a. Systolic blood pressure  $\leq 90$  mmHg
  - b. Heart rate  $>100$  BPM

*Exclusion Criteria:*

- (1) Ground level fall.
- (2) Penetrating pelvis injury without frank evidence of fracture.
- (3) Obviously pregnant patients
- (4) Patients who are too small ( $<32$ in) or too big ( $>50$ in) for the binder
- (5) Priority 2 or 3 Trauma

*Representativeness of the Sample:* Our study should capture a large portion of the patients who present to the hospital with pelvic trauma. We chose to exclude patients who sustained a ground level fall. These are low-energy mechanisms of injury less likely to be improved by external pelvic compression, and more likely to have skin compromise.

Definition of Variables:

*Primary Outcome Variables:* These variables will be abstracted from the medical record by research staff.

- (1) Initial heart rate and blood pressure at the scene (pre-hospital)
- (2) Initial heart rate and blood pressure upon arrival at the Emergency Department
- (3) Time of injury, EMS arrival, binder application (if done), ED arrival
- (4) Initial labs upon arrival at the Emergency Department: lactate, base deficit, PT/INR, hemoglobin
- (5) 24-hour transfusion requirements
- (6) 48-hour transfusion requirements
- (7) Need for angioembolization
- (8) Need for surgical control of bleeding
- (9) Length of intensive care unit stay
- (10) Length of hospital stay
- (11) Need for readmission
- (12) 30-day mortality
- (13) Location of pelvic binder upon presentation to the hospital
- (14) Time the binder removed
- (15) Skin compromise attributable to binder use (location and time since binder placement)
- (16) Other complications of binder use (description and time since binder placement)

*Secondary Outcome Variables:* These variables will be reported by non-obtunded patients using a Visual Analog Score in the pre-hospital environment.

- (1) Pain score at presentation
- (2) Pain score at the conclusion of ambulance transfer (upon arrival to the Emergency Department)

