*Randomization:* Prior to each shift, each ambulance will be randomly assigned an opaque box containing either a commercial pelvic binder or a weight-equivalent object and patient ID tag. When an ambulance arrives at the scene, EMS personnel will apply inclusion and exclusion criteria to determine if the patient is appropriate for this study. If so, EMS personnel will open the opaque box. If the box contains a pelvic binder, the patient will have a pelvic binder placed. If the opaque box contains the weight-equivalent object, the patient ID tag will be clipped to the patient, and the patient will be managed without a binder under the current standard of care. At the receiving facility, EMS personnel will page the research team and fill out the label on the box with information identifying the run number, unit number, and time of dispatch. The box will be placed in a box in the emergency department for research staff to pick up. The removal of pelvic binder on patient will be determined by the appropriate physician team. Pelvic binder should be removed within 72 hours of admission.

*Collection of prehospital outcome data:* At the time of initial assessment by EMS personnel, awake patients will be asked to rate their pain using a visual analog scale (VAS). At the conclusion of ambulance transport, awake patients will again be asked to rate their pain using a VAS. The patient's initial heart rate and blood pressure will also be recorded in the prehospital environment.

*Collection of data in the hospital environment:* Patients enrolled in the study will be identified using the information collected by EMS personnel on the box, the page to research staff, and/or the presence of a pelvic binder or patient ID tag on the patient. Primary outcome data will be abstracted from the medical record. The patient's initial heart rate and blood pressure will be recorded upon presentation to the Emergency Department (ED). Other laboratory data, including lactate, base deficit, hemoglobin, and PT/INR, will be collected upon presentation to the ED. Pelvic radiographs will be obtained as appropriate per standard of care. Both placement and location of the pelvic binder upon arrival will be determined from pelvic radiographs. Whether or

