**PATCH – Pelvis Protocol v5**  
**12/20/16**

not the pelvic binder is removed in the ED is based on clinical data (clinical evidence of hemodynamic stability, imaging failing to demonstrate a pelvic fracture) and is at the discretion of the treating physician (generally an emergency medicine physician or trauma surgeon) in the ED. Patients with evidence of hemodynamic instability or concern for ongoing hemorrhage will undergo angioembolization or surgical intervention according to our institution's protocol. Twenty-four and 48-hour transfusion requirements (including packed red blood cells, fresh frozen plasma, platelets, and cryoprecipitate); need for endovascular or surgical intervention for control of hemorrhage; and length of intensive care unit and hospital stay will be determined from the medical record. Thirty days after the injury, the need for readmission and all-cause mortality within this period will be recorded. Demographic and medical variables (BMI, history of cardiac disease, anticoagulant use, initial PT/INR) will also be abstracted from the medical record.

Complications of binder use, including skin compromise, will also be identified, as will the length of time between binder placement and each event. Should such an event occur a formal incident report will be filed with the appropriate hospital agency as well.

The fracture classification will be assigned by a fellowship-trained orthopaedic traumatologist. The type and timing of operative fixation of the patient's pelvic injury, if necessary, will be at the discretion of the treating orthopaedic surgeon.

*Data analysis:* Data analysis will be carried out when all patients have been assigned to either the experimental or control group. In order to determine whether the randomization process produced comparable groups, we will use t-tests and cross-tabulations to compare patients randomized to the pelvic binder group with those randomized to the control group. The following variables will be considered: age, gender, BMI, history of cardiac disease, anticoagulant use, PT/INR at presentation, injury severity score, and Young and Burgess pelvic fracture class. An intention to treat analysis will also be performed.

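### Could the analysis start before 30-day mortality and readmission are known for the last patients?

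*Combined protocol and SAP*

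**What the plan says.** All places are in the combined protocol and SAP.

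- **Methodology, Data analysis.** The only sentence on timing is "Data analysis will be carried out when all patients have been assigned to either the experimental or control group". It leads into a check of baseline comparability and a statement that an intention-to-treat analysis will be done. There is no sentence on data lock or on open follow-up.
- **Methodology, Randomization.** Allocation reaches the vehicle first: "Prior to each shift, each ambulance will be randomly assigned an opaque box". Eligibility comes next: "When an ambulance arrives at the scene, EMS personnel will apply inclusion and exclusion criteria". The patient then enters a group: "If so, EMS personnel will open the opaque box".
- **Methodology, Collection of data in the hospital environment.** "Thirty days after the injury, the need for readmission and all-cause mortality within this period will be recorded".
- **Definition of Variables, Primary Outcome Variables.** The list includes "11) Need for readmission" and "12) 30-day mortality". The Purpose of the Study also closes its list of primary outcomes with "and length of ICU stay) and 30-day mortality".

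**The concern.** The timing sentence is tied to assignment, and assignment is finished at the roadside. Whether it is dated from the pre-shift allocation of the box or from its opening, it is over by day 0 of the last patient. Two listed primary outcome variables are not final until day 30. Others also build up after assignment: 24- and 48-hour transfusion, intensive care stay and hospital stay.

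An analyst who took the sentence as a starting signal would hold incomplete values for the most recent patients. Someone alive on day 5 might be counted as a 30-day survivor, which would understate mortality, or might be dropped. The plan does not choose between these. At stake would be lost information on primary outcomes and, in principle, an early look followed by a second one once follow-up closed.

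**Working it through.** The plan states no figure on this point (no sample size, accrual period or event count), so there is nothing to reproduce. The check has two parts.

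**1. Can the timing sentence be a starting signal?**

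Set the sentence beside the variables that its own paragraph says will be compared, and ask when each exists.

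| Variable in the comparability check | Source in the protocol | Exists when the box is opened? |
|---|---|---|
| PT/INR at presentation | Emergency department labs | No |
| Injury severity score | Orthopaedic surgeon, from medical record data | No |
| Young and Burgess class | Orthopaedic traumatologist | No |

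The first analysis described could not be run for the last patient at the moment the literal condition is met. The sentence therefore makes sense only as a lower bound: nothing is analysed until the last patient is in.

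This alone does not carry the analysis to day 30, since labs and classification come much sooner. The second step comes from the data collection section. It requires readmission and all-cause mortality to be recorded 30 days after injury, without excepting late entrants. A 30-day mortality variable for the last patient cannot be completed before that patient's day 30. A team that carries out the whole plan therefore has these data before it can analyse them.

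**2. What would the literal reading cost?**

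Assumptions, none from the documents: uniform accrual over 6, 12, 24 or 36 months, a month of 30.4 days, and a mean event day of 3 or 15 for events within 30 days.

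Accrual length is A = months × 30.4, giving 182.4, 364.8, 729.6 and 1094.4 days.

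- Share of patients with an open 30-day window at the last assignment = 30/A. For 6 months, 30/182.4 = 16.4%.
- Share with an open 48-hour transfusion window = 2/A. For 6 months, 2/182.4 = 1.1%.
- Share of 30-day events still to come. A patient assigned u days before the cut-off has a future event if the event day exceeds u. With u uniform on 0 to A, the share is (mean event day)/A. For 6 months, 3/182.4 = 1.6% and 15/182.4 = 8.2%.

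| Accrual | Open 30-day window | Open 48-hour window | Events to come, mean day 3 | Events to come, mean day 15 |
|---|---|---|---|---|
| 6 months | 16.4% | 1.10% | 1.6% | 8.2% |
| 12 months | 8.2% | 0.55% | 0.8% | 4.1% |
| 24 months | 4.1% | 0.27% | 0.4% | 2.1% |
| 36 months | 2.7% | 0.18% | 0.3% | 1.4% |

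The first column counts patients whose window is open, not outcomes lost. Events already recorded would still count. The cut-off would apply to both arms alike, so the table shows lost information and gives no evidence of bias between arms. The 8.2% figure needs both the shortest accrual and the later event timing.

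**The case for a change.** The best case for a change is that unstated intent binds nobody. This is the plan's only timing rule, and an analyst could follow it to the letter while using unfinished primary outcomes. The plan has no censoring method, missing-data rule or outcome model to absorb them. The only tests it names, t-tests and cross-tabulations, are for baseline comparability. With no lock date, nothing in writing forbids a look when enrolment closes and another a month later. The remedy looks nearly free: one sentence and a wait of about 30 days.

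Part of this stands. No passage makes completed follow-up or a data lock a condition, and the order of steps is left to inference.

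The rest is weaker. Early analysis requires the analyst to read one sentence apart from both its own paragraph and the data collection section. Nothing in the documents suggests an early look is planned. The remedy is also less tidy than it seems. Intensive care and hospital stay have no 30-day cap, so a day-30 trigger would leave stay unfinished for anyone still in hospital. The wait would also include the time needed to lock the data.

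**Conclusion.** No change to the plan is needed. The timing sentence names enrolment rather than follow-up as its milestone, but read with the rest of the Methodology it means that analysis does not begin before enrolment is complete. The required 30-day recording supplies the remaining condition. This is a gap in stated order that analysts fill sensibly, not a contradiction and not a planned premature analysis.

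Even on the literal reading, the share of 30-day events missed would be 0.3% to 8.2%, and the share of patients with an open 48-hour transfusion window 0.2% to 1.1%. Those ranges rest wholly on assumed uniform accrual over 6 to 36 months and, for events, on an assumed mean event day of 3 or 15. They illustrate the point and are not estimates for this trial. The conclusion itself rests on the text: the comparability variables rule out the literal trigger, and the 30-day recording applies to every patient.

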**PATCH – Pelvis Protocol v5**  
**12/20/16**

*Potential Confounding Variables*

The following variables will be abstracted from the medical record by research staff:

- (1) Age
- (2) Gender
- (3) Body mass index
- (4) Comorbidities (history of diabetes or cardiac disease)
- (5) Anticoagulant use

The following variables will be determined by an orthopaedic surgeon based on data abstracted from the medical record:

- (6) Injury severity score
- (7) Fracture severity: defined by the Young and Burgess and AO/OTA classification of pelvic fractures

Methodology

*Application of inclusion and exclusion criteria:* Awake patients will be asked at the scene for their age (inclusion criteria 1), mechanism of injury (inclusion criteria 2), and presence of pelvic, hip, or groin pain (inclusion criteria 3). Patients who state they sustained a ground level fall will be excluded (exclusion criteria 1). The age of obtunded patients will be determined using personal identification (e.g. driver's license) if available but will otherwise be estimated by EMS personnel. EMS personnel will evaluate patients for signs of pelvic injury (inclusion criteria 4) and hemodynamic instability (inclusion criteria 5). Based on the location of the scene and severity of the injuries, EMS personnel and their dispatcher will determine whether participating hospital or a different facility will receive the patient (exclusion criteria 2).

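### The randomisation check includes ED-arrival PT/INR, a listed primary outcome measured after the binder, and omits scene heart rate, scene blood pressure and first pain score, which are filed as outcomes

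*Combined protocol and SAP*

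**What the plan says.** The Data analysis paragraph under Methodology gives the purpose of the comparison: "In order to determine whether the randomization process produced comparable groups". The method is t-tests and cross-tabulations, and the variables are "age, gender, BMI, history of cardiac disease, anticoagulant use, PT/INR at presentation, injury severity score, and Young and Burgess pelvic fracture class".

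PT/INR appears in three other places:

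- Primary Outcome Variables, item 4: "Initial labs upon arrival at the Emergency Department: lactate, base deficit, PT/INR, hemoglobin".
- Collection of data in the hospital environment, on timing: "Other laboratory data, including lactate, base deficit, hemoglobin, and PT/INR, will be collected upon presentation to the ED".
- The same section, as a patient characteristic: "Demographic and medical variables (BMI, history of cardiac disease, anticoagulant use, initial PT/INR) will also be abstracted from the medical record".

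Scene heart rate and blood pressure are Primary Outcome Variable 1. The first pain score is Secondary Outcome Variable 1, reported by non-obtunded patients and taken when EMS personnel first assess them. None of these is among the Potential Confounding Variables or in the comparability list.

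On sequence, EMS personnel apply the eligibility criteria at the scene, including haemodynamic instability defined by systolic pressure and heart rate. The Randomization paragraph then continues: "If so, EMS personnel will open the opaque box". Any binder is placed at that point, before arrival at hospital.

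**The concern.** A check on randomisation is informative only for variables that the treatment cannot have changed. PT/INR on arrival fails that test. The trial's hypothesis is that the binder reduces haemorrhage and the need for resuscitation, and the plan itself lists arrival PT/INR among the outcomes. The same number is thus asked to show both that the groups started alike and whether the binder worked.

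Two misreadings are possible. A real binder effect on PT/INR could be reported as failed randomisation. Alternatively, a treatment effect could offset a chance imbalance, and the resulting similarity could be taken as reassurance.

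The omission is the mirror image. A value recorded before the binder goes on cannot measure its effect, yet three such values are filed as outcomes and left out of the check. Background and Significance links hypotension at the scene and on arrival to higher mortality, so the check leaves out a severity measure that the protocol treats as prognostic. This matters more because boxes are assigned to ambulances before the shift and EMS personnel decide at the scene who is enrolled. Scene physiology is then the most direct evidence that the patients enrolled in each arm were alike before treatment.

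**Working it through.** **Roles and timing.** The plan gives no figure to reproduce here. The test is to set each variable's place in the lists against the time it is measured.

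| Variable | Measured | Before or after the binder | Outcome list | Confounder list | Comparability list |
|---|---|---|---|---|---|
| PT/INR | ED arrival | After | Primary, item 4 | No | Yes |
| Scene heart rate | First EMS contact | Before (inferred) | Primary, item 1 | No | No |
| Scene blood pressure | First EMS contact | Before (inferred) | Primary, item 1 | No | No |
| First pain score | Initial EMS assessment | Before (inferred) | Secondary, item 1 | No | No |

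The comparability list has 8 variables: age, gender, BMI, cardiac history, anticoagulant use, PT/INR, injury severity score and Young and Burgess class. One of the 8 is a listed primary outcome. None of the 3 scene values is included.

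The entries marked as inferred rest on three things: the scene vital signs are called initial, the pain score is tied to the initial assessment, and haemodynamic status is needed for eligibility before the box is opened. The plan does not say that the recorded values are the pre-opening ones. Because boxes are assigned before the shift, these values come after formal allocation but before it is revealed, so pre-intervention is the exact term.

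**Precision available from the scene values.** Let r be the correlation between a scene value and its arrival value. The documents give no r, so I assume 0.3 to 0.7. I also assume independent patients and, for the change score, equal standard deviations at scene and arrival. The variance of the difference between arms, relative to comparing arrival values alone (1.00), is:

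- arrival value adjusted for scene value: 1 − r²
- change from scene to arrival: 2(1 − r)
- confidence interval width under adjustment: √(1 − r²)

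| r | Adjusted, 1 − r² | Change, 2(1 − r) | Interval width, √(1 − r²) | Narrower by |
|---|---|---|---|---|
| 0.3 | 1 − 0.09 = 0.91 | 2 × 0.7 = 1.40 | 0.954 | about 5% |
| 0.5 | 1 − 0.25 = 0.75 | 2 × 0.5 = 1.00 | 0.866 | about 13% |
| 0.7 | 1 − 0.49 = 0.51 | 2 × 0.3 = 0.60 | 0.714 | about 29% |

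The equal-SD assumption affects only the size of the change-score figures. If k is the ratio of scene SD to arrival SD, the change score has relative variance 1 + k² − 2rk. Subtracting 1 − r² leaves (k − r)², which is never negative. At k = 1 it is 0.49, 0.25 and 0.09, matching the gaps between the two variance columns. Adjustment is therefore never less precise than the change score, whatever the two SDs.

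**The case against.** The strongest reply is that this is mostly a matter of labels.

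- **The primary outcome list is an inventory.** It also holds event times, binder location and removal time. Purpose of the Study, which describes the primary outcomes in prose, does not name PT/INR. Both points are true. But the outcome list does name it, and even if it did not, a value drawn after the binder could not test randomisation.
- **PT/INR may be meant to capture pre-existing coagulopathy.** It is placed beside anticoagulant use, which suggests so. Anticoagulant use is already in the list and serves that purpose without being open to treatment effects.
- **Little hangs on the check.** No decision, threshold or adjustment follows from it. This stands and limits the severity. It is also true that no balance test can prove that randomisation worked. The problem specific to PT/INR is that a treatment effect can create or hide a difference.
- **No stated analysis uses any outcome, so the scene values are not singled out.** Beyond a sentence promising an intention-to-treat analysis, no outcome comparison is described. That is a larger gap, but it does not explain why the scene values are absent from a comparability list that is written out.
- **The variance figures do not measure the main defect.** Correct. They rest on an assumed r and support only the recommendation to adjust.
- **Injury severity score and fracture class are also assigned after arrival.** This extends the point; it does not answer it. Both are meant to describe the original injury, so the case against them is weaker than for PT/INR.

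**Conclusion.** The concern holds. As written, the plan uses a post-intervention value, listed as a primary outcome, as 1 of 8 checks on randomisation. It uses none of the 3 scene values that could properly serve.

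The consequence is misinterpretation, not bias in a stated analysis. The size of any binder effect on PT/INR cannot be derived from the documents. The finding on PT/INR needs no assumption. Treating the scene values as baseline rests on their being recorded before the box is opened, which the sequence implies but the plan does not state. The precision gain depends on the assumed r and is a secondary benefit. This should be corrected, but it does not threaten the trial's validity by itself.

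**What to change.** 1. Remove PT/INR from the comparability list and from the phrase on demographic and medical variables. Keep it as an outcome, and leave anticoagulant use in the list.
2. Reclassify scene heart rate, scene blood pressure and the first pain score (non-obtunded patients) as baseline variables and add them to the baseline comparison. State that the recorded values are those taken before the box is opened.
3. As a recommendation for precision, analyse ED heart rate, ED blood pressure and arrival pain score with the matching scene value as covariate, in preference to a change score.

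Items 1 and 2 are wording only: the variable lists, the Data analysis paragraph and one sentence on recording order. Item 3 adds one covariate to the models for three arrival measures. Every variable is already collected.
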